2.5 Economic analysis

Economic evaluation of DBT

We will undertake a detailed study of the cost of screening with 2DDM and with DBT and either S2D or 2DDM. Capital and maintenance costs related to screening technologies will be obtained from the manufacturers or finance departments at the screening centres and amortized appropriately according to predicted lifetime. Staff costs and overheads for screening centres and image reading centres will be derived from centre finance departments. The time taken to record images with each screening modality, and the time to read images will be determined and combined with centre costs to estimate a total cost per mammographic screen for each of the screening centres in the trial. Costs associated with follow-up of a positive screen will be determined in consultation with screening centres. Patient costs will be estimated on the basis of typical attendance times valued at average gross wage rate along with estimates of average travel costs.

We will undertake a cost-utility analysis of DBT + S2D (or 2DDM) compared to current practice (2DDM). The primary analysis will consider an NHS perspective and include future related costs of screening (diagnosis and treatment of Breast cancer). A societal perspective which includes patient costs of attending screening and follow-up will be examined in a sensitivity analysis. The primary analysis will consider the costs and consequences of Breast screening with either modality over the trial follow-up period. We will estimate the impact on health and treatment costs of cancers detected by predicting treatment costs and mortality according to age and prognostic factors at diagnosis. Mortality will be weighted for quality of life to estimate the Quality Adjusted Life-Years (QALYs) lost to Breast cancer in each arm. A QALY is measure of health outcomes which combines longevity and quality of life. If overall costs are higher in the DBT arm the data will be combined to estimate an Incremental Cost-Effectiveness Ratio (ICER) for DBT and allow comparison against accepted thresholds of £20,000 to £30,000 per QALY. The trial data will be bootstrapped (a resampling technique to quantify the impact of uncertainty in the data) and the results presented as a Cost-Effectiveness Acceptability Curve (CEAC). The CEAC plots the probability an intervention is cost-effective according to the value placed on the health outcome and after allowing for sampling uncertainty.

In addition to this analysis we will build a simulation model of Breast cancer. The model will utilize data on costs, sensitivity and specificity of each screening modality taken from the trial data along with data from the literature on the natural progression of Breast cancer to estimates costs associated with screening and treatment of Breast cancer and quality adjusted life-expectancy over women’s lifetimes. The model will fully incorporate uncertainty around parameter estimates and the main outputs will be the mean ICER across simulations and the CEAC.

3. Sample Size, Selection and Withdrawal of Subjects

Recruitment.

Up to 09.2023, the trial has recruited over 36,000 women from 6 screening centres, randomized 1:1 between the control group (standard 2DDM) and the intervention group (DBT and 2DDM/synthetic 2D). Two further sites are starting recruitment this autumn – Leicester, St George’s London. We do not anticipate increasing the number of trial sites above 8.

The overall recruitment rate is just over 50% of those who attend screening and are invited to participate. The participation rate varies between the sites (26%-81%) and reflects differences in the local population demographics. Participation is higher at static sites compared to mobile screening sites. We have examined ways of increasing participation rates including

- different consent processes – face to face, phone and online;
- revision of the patient information materials;
- investment in staff time to facilitate consenting.

We estimate that trial recruitment will continue at between 1500 and 2000 per month with 8 recruiting sites.

Randomization ratio.

We have therefore considered changing the randomization ratio in favour of the intervention arm and decreasing the overall recruitment target. We conclude that the randomization ratio could be changed to 1:3 (control:intervention) and the overall target recruitment changed to 70,000. This would provide sufficient data to address the impact of DBT screening on interval cancer rates and cancer detection. We plan to augment the trial analysis with a further secondary analysis, comparing endpoints between our intervention group and figures from the national programme, using standardised incidence ratios.

Table 1. Estimate of numbers recruited in control and intervention groups to 03.2025, with a 1:3 randomization ratio from 01.2024

			Control	Intervention	Total
To 09.2023			18,000	18,000	36,000
To 12.23			20,000	20,000	40,000
01.24 - 03.25 @1:3	control	intervention			
1500/month	5625	16,875	25,625	36,875	62,500
2000/month	7500	22,500	27,500	42,500	70,000

Invasive cancer detection rates.

For a comparison of invasive detection rates (the first primary endpoint), if we posit 9 per thousand in the DBT arm and 7 in the control, we will have approximately 80% power with the totals assuming recruitment of 1,500 per month and in excess of 80% power with 2,000 per month (5% significance level, 2-sided testing). Thus even without the use of the routine screening data, we will have sufficient power for the first primary endpoints.

Interval cancer rates.

Assuming the national rate of interval cancers in the control group, 3.5 per 1000 over 3 years, and if we assume conservatively that the reduction is 25% less than the increase in invasive detection rates, we would anticipate a rate of 2 per 1000 in the intervention arm.

Our totals for recruitment of 1,500 per month would yield in excess of 90% power to detect this as significant (5% significance level, two-sided testing). Thus we will be powered for this too.

As noted above, we also propose to carry out age-standardised comparison of these endpoints with those observed nationally, since the latter give highly precise estimates of outcomes for usual care. However, we re-emphasise that the primary analyses will be the protocol-specified randomised trial comparisons.

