Address: Breast Imaging SWLBSS Rose Centre, St George's University Hospitals NHS
Foundation Trust, [name]

Email: [contact]

1. Introduction

2 Trial Objectives, Design and Statistics

- 2.1. *Trial Objectives*
- 2.2 *Trial Design*
- 2.3 *Trial Flowchart*
- 2.4 *Trial Statistics*
- 2.5 *Economic analysis*

3. Sample Size, Selection and Withdrawal of Subjects

- 3.1 *Inclusion*
- 3.2 *Exclusion*
- 3.3 *Criteria for Premature Withdrawal*

4. Study procedures

- 4.1 *Informed Consent Procedures*
- 4.2 *Randomisation Procedures*
- 4.3 *End of Study Definition*

5. NHS Breast Screening Services - trial procedures

- 5.1 *Mammography Examinations*
- 5.2 *Image Storage*
- 5.3 *Mammography Film Reading*
- 5.4 *Results of Mammography Film Reading*
- 5.5 *Data Recording/Reporting*
- 5.6 *Image Transfer to Other Sites*
- 5.7 *Trial Site Service Quality*

6. Assessment of Safety

- 6.1 *Risk from Ionising Radiation*
- 6.2 *Ethics Reporting*

7. Trial Steering Committee

8. Ethics & Regulatory Approvals

9. Data Handling

- 9.1 *Confidentiality*
- 9.2 *Trial Participant Data Record*
- 9.3 *Archiving*
- 9.4 *Compliance*
- 9.5 *Clinical Governance Issues*
- 9.6 *Non-Compliance*

10. Finance & Publication Policy

Study Synopsis

Title	Prospective Randomised Trial of Digital Breast Tomosynthesis (DBT) Plus Synthetic 2D Mammography (S 2D) compared to Standard 2D Digital Mammography in Breast Cancer Screening.
Protocol Short Title/Acronym	PROSPECTS
Protocol Version number and Date	Version
Is the study a Pilot?	No
Study Duration	Seven years
Methodology	Randomised controlled trial
Sponsor Name	King's College Hospital NHS Foundation Trust
Chief Investigator	[name] [name]
REC Number	17/LO/0054
IRAS Number	199080
Medical Condition or Disease under Investigation	Breast Cancer
Purpose of Clinical Trial	To measure the cost-effectiveness of DBT and S2D compared to standard 2DDM in breast cancer screening
Primary Objective	To compare the cost-effectiveness of breast cancer screening using DBT + S2D with screening using 2DDM by measuring cancer detection rates, interval cancer rates, size and lymph node status of Grade 2 and 3 invasive cancers in intervention (DBT + S2D) and 2DDM (standard care) groups.

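### The lifetime model's main output is worded as an average of per-simulation ICERs, which does not estimate mean incremental cost over mean incremental QALYs

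*Protocol*

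**What the plan says.** Section 2.5 describes two economic analyses.

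The first is a within-trial cost-utility analysis, which the section calls primary: "The primary analysis will consider the costs and consequences of Breast screening with either modality over the trial follow-up period". Its ICER is conditional on the sign of the cost difference ("If overall costs are higher in the DBT arm the data will be combined to estimate an Incremental Cost-Effectiveness Ratio (ICER) for DBT") and is to be set against "accepted thresholds of £20,000 to £30,000 per QALY". The trial data are bootstrapped and shown as a CEAC.

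The second is a lifetime model, introduced with "In addition to this analysis we will build a simulation model of Breast cancer". The protocol says of it: "The model will fully incorporate uncertainty around parameter estimates", and then "the main outputs will be the mean ICER across simulations and the CEAC".

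The section does not say that the model's ICER is a ratio of two means. It gives no rule for simulations in which the QALY difference is zero or negative, and it does not mention net monetary benefit. The synopsis states the primary objective as "To compare the cost-effectiveness of breast cancer screening using DBT + S2D with screening using 2DDM", and section 2.1 lists cost-effectiveness among the primary end-points.

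**The concern.** In a model that propagates parameter uncertainty, each simulation gives its own incremental cost (ΔC) and incremental QALYs (ΔQ). A threshold in pounds per QALY is meant to be compared with expected cost over expected QALYs, E[ΔC]/E[ΔQ]. The wording instead asks for the average of ΔC/ΔQ over simulations, which is a different quantity.

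A few simulations with ΔQ close to zero can dominate that average, and running more simulations does not cure this. The average also loses the meaning of the sign: dominant and dominated simulations both give negative ICERs and are pooled as if alike.

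The model is the only analysis described that follows costs and quality-adjusted survival over a lifetime. A misleading point estimate from it would weaken the long-run evidence on the primary objective.

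**Working it through.** The protocol states no incremental cost, incremental QALY or ICER, so there is no figure to reproduce. The check compares the two estimators under stated assumptions.

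**1. Direction of the error.** If ΔC and ΔQ are independent, E[ΔC/ΔQ] = E[ΔC] × E[1/ΔQ]. For a small CV of ΔQ, E[1/ΔQ] ≈ (1/E[ΔQ]) × (1 + CV²). With a true ICER of £20,000 and a positive mean cost difference:
- CV 0.1: 20,000 × 1.01 = £20,200
- CV 0.2: 20,000 × 1.04 = £20,800

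The expansion is only local. A normal ΔQ has density at zero, so strictly E[1/ΔQ] does not exist. At small CV this does not show in practice; at larger CV it does.

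**2. A plausible CV.** The protocol does not give the CV of ΔQ. As a rough proxy, take SE/difference for the trial inputs, using the planning rates in section 2.3 and the arm sizes at 1,500 recruits per month (25,625 control, 36,875 intervention).
- Detection, 7 against 9 per 1000: SE = √(0.007 × 0.993/25,625 + 0.009 × 0.991/36,875) = 0.000716; 0.000716/0.002 = **0.36**
- Interval cancers, 3.5 against 2 per 1000: SE = √(0.0035 × 0.9965/25,625 + 0.002 × 0.998/36,875) = 0.000436; 0.000436/0.0015 = **0.29**

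Natural-history inputs from the literature may add uncertainty.

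**3. Simulation.** Assumed, not from the protocol: ΔC normal with mean £20 and SD £5; ΔQ normal with mean 0.0010; independent; true ICER 20/0.0010 = £20,000. There were 2,000 reruns of 5,000 draws at each CV.

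| CV of ΔQ | Mean of ICERs, 95% range across reruns | Negative reruns |
|---|---|---|
| 0.1 | £20,060 to £20,370 | – |
| 0.2 | £20,700 to £21,100 | none |
| 0.29 | about £18,900 to £25,000 | 0.3% |
| 0.36 | about £3,400 to £41,300 | 2% |
| 0.5 | about −£39,000 to +£153,000 | 8% |

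The ratio of means stayed within about £19,800 to £20,200 at CV 0.29 and 0.36, and within £19,600 to £20,430 throughout. The median of the averaged ICERs was £20,920 at CV 0.2 and £22,700 at CV 0.3, so the usual error is upward. The limits at the higher CVs are themselves unstable: a second batch at CV 0.5 gave −£52,000 to +£111,000, with 9% negative.

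**4. A second set of assumptions.** With ΔC of mean £30 and SD £8, ΔQ of mean 0.0015 (again £20,000 per QALY), and 20 reruns of 10,000 draws, the full range of the averaged ICER was £20,100 to £20,300 at CV 0.1, £18,400 to £29,400 at CV 0.3, and −£99,800 to £78,700 at CV 0.5. The share of draws with ΔQ at or below zero was 0.04% at CV 0.3 and 2.3% at CV 0.5. The CEAC value at £20,000 stayed between about 0.49 and 0.51 at every CV from 0.1 to 1.0.

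**5. Sign.** 30/0.0015 and (−30)/(−0.0015) both equal £20,000 per QALY, yet they call for opposite decisions.

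**The case against.** The best defence is that the phrase is shorthand. Many analysts who write it compute the ratio of means, and the detail may sit in an analysis plan that is not shown. That is possible. But the protocol does not leave the estimator open; it names one, and the natural reading is an average of ratios. If it is shorthand, the same edit settles it.

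Three stronger readings are tempting, and the protocol does not support them.
- A reader might infer that the trial's main cost-effectiveness result is unstable. The threshold comparison is attached to the within-trial analysis, whose ICER is not described as a mean of ratios. The model is additional to it, and no threshold is tied to the model's averaged ICER.
- A reader might infer that the conditional within-trial ICER leaves no decision rule if DBT is cheaper but less effective. The bootstrap and CEAC are unconditional and cover every combination of signs. Withholding a bare ICER when DBT is cheaper is defensible.
- A reader might infer that wild values are certain because QALY gains per woman are small in screening. Absolute size is not what matters; the CV is, and it is not given.

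It is also fair that the draws were independent normals, whereas the model will derive costs and QALYs from shared sensitivity and specificity inputs. The ranges are illustrations, not forecasts.

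**Conclusion.** The point holds as a wrongly worded estimator for one main output of the supplementary lifetime model. The mathematical objection does not depend on the assumptions; its size does. It is negligible to small (about 1% to 5%) if the CV of the QALY difference is 0.1 to 0.2. At the rough proxies of 0.29 and 0.36, reruns of an identical model could differ by several thousand pounds per QALY at the lower value, and by more than the whole width of the £20,000 to £30,000 band at the higher. Frequent sign changes need a CV of about 0.5, which no figure in the protocol supports. The primary within-trial ICER and both CEACs stand, so a decision-maker would still have a usable answer.

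**What to change.** In the last sentence of section 2.5, replace the averaged ICER with: *the ICER calculated as mean incremental cost divided by mean incremental QALYs across simulations*. Keep the CEAC. Optionally add mean incremental net monetary benefit at £20,000 and £30,000 per QALY with a 95% interval, which stays well defined whatever the signs of the cost and QALY differences. The within-trial paragraph needs no change on this account. The cost is one phrase: the same simulation output serves, with no new data or modelling.

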3.1 Inclusion Criteria

- Women aged 49-71 years attending for routine breast screening using x-ray mammography.
- Able to provide informed consent.

3.2 Exclusion Criteria

- Women aged less than 49 years or more than 71 years (these women may already be taking part in the National Age Extension Screening Trial)
- Women unable to provide informed consent.

3.3 Criteria for Premature Withdrawal

Women who consent participate in this trial will undergo either 2DDM + DBT. Following mammography, there are no further trial specific investigations and we do not therefore foresee instances of premature withdrawal from the trial.

4. Study procedures

4.1 Informed Consent Procedures

- All eligible women who are to be invited to participate in the trial will be sent written information about the trial. . This information will either be sent by post or emailed.
- The majority of potentially eligible women will be contacted by telephone prior to screening appointment, she will be asked whether she has received the written trial information and whether she is willing to participate in the trial.
- Women will be advised to read all the information including the consent form and make a decision of whether to participate prior to attendance for screening.

There are a number of options available for consenting as outlined below:

Option 1: e-consenting - Women receive the trial information and/or are contacted by a member of the PROSPECTS team. If a women decides that she would like to consent, she may visit the PROSPECTS website or go directly to the e-consenting portal URL (details of this are provided on the PIS). At the end of the consent form, there will be an option to enter an email address where a confirmation email and her consent form will be sent, alternatively she can contact the trial site to request a copy of the form to be posted. If personal electronic devices and the internet are not accessible, the e-consenting process may be possible by using a PROSPECTS iPad/Tablet at sites that have adequate time and space available to facilitate this. Women may contact the site if she requires assistance with this. If a women has e-consented less than 48 hours prior to her appointment, she must bring confirmation with her, as the list of those consented is exported in advance.

Option 2: Over the phone paper consent - If women are contacted by the research team over the phone, she may be given the opportunity to consent over the phone either at the initial time of contact or at a later date arranged. She must have a paper consent form which she may have received through the post or electronically. She may complete the form whilst on the phone to the research team and must bring this form with her or scan the completed form to the research team in advance. The research team will keep a record of those who have consented over the phone which will be shared with relevant sites. The names on any paper forms which are brought in will be checked against the list provided by the research team, collected and scanned. The scanned pdf's will be sent to the research team. They will then populate with an electronic signature and these forms will be saved. If women would like a copy of their signed form, they will request this by contacting the research team using the details provided on the PIS.

Due to the COVID-19 pandemic, at some trial sites, infection control regulations may not allow paper forms to be used at all. In these cases, e-consenting must be used as an alternative.

Option 3: Women has pre-signed a consent form, but has had no contact with the research team - In cases where the research team have been unable to contact a women and she arrives with a completed consent form, the mammography staff will simply verify the signature is their own and countersign. If option 3 occurs in sites where paper forms are not allowed, the option to e-consent may be available if time allows, otherwise she will not be allowed to join the trial.

Option 4: Women has not had contact with the research team and has not consented – Some sites will have adequate space and time available to facilitate a face to face consenting option. When a women arrives and time allows, she may be provided with trial information and a trial conversation may take

place. Resources may be available at these sites such as iPad/tablets, PIS, PIL and paper consent forms (subject to site specific infection control policy). If a women decides to consent, the site staff can facilitate this process and countersign the paper consent form or provide an electronic device for e-consenting.

- If a woman declines to participate, she will be offered standard 2D digital mammography screening.
- If a woman accepts the invitation to participate, she will undergo either standard 2DDM/S2D and DBT according to the clinic randomisation procedure. After the first 25,000 women have undergone 2DDM and DBT, women entered into the interventional arm will undergo DBT and S2D.
- Women will no longer be provided a copy of the consent form at their appointment, if a women wishes to receive either an electronic or paper version of the consent form, she must contact the site using contact details on the PIS.

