2.1. Trial Objectives

Primary objectives.

To compare the cost – effectiveness of breast cancer screening using DBT + S2D with screening using 2DDM by measuring cancer detection rates, interval cancer rates, size and lymph node status of Grade 2 and 3 invasive cancers in intervention (DBT + S2D) and 2DDM (standard care) groups.

Secondary objectives.

1. To demonstrate non-inferiority of DBT + S2D compared to DBT + 2DDM.
2. To measure the impact of DBT +2DDM or S2D screening on screening recall rates, benign biopsy rates at diagnostic assessment and at surgery.
3. To measure the effect of DBT + 2DDM or S2D screening compared to 2DDM in patient groups according to breast density, type of screen, age.
4. To develop methods for measuring reader performance with DBT + 2DDM or S2D screening.

5. To carry out retrospective reader studies to measure the effect of other screening strategies – 2DDM vs DBT alone, 2DDM vs DBT + synthetic 2D, 2DDM vs 2DDM + limited tomosynthesis views.
6. To compare patient preferences for breast cancer screening with DBT +2DDM or S2D vs 2DDM.
7. To develop & evaluate Artificial Intelligence Algorithms for the Analysis of DBT images.

Primary end-point.

Invasive cancer detection rates

Interval cancer rates

Size and lymph node status of grade 2 and 3 invasive cancers

Cost-effectiveness of screening with DBT + 2DDM or S2D vs screening with 2DDM.

Secondary end-point.

[figure not shown]
1. Measurement of invasive cancer detection rates using DBT + 2DDM or S2D vs 2DDM
2. Recall rates
Benign biopsy rates at assessment
Benign surgical biopsy rates
3. Measurement of cancer detection rates, recall rates in subgroups of women in intervention and control groups defined by breast density, type of screen, age group.
4. Development of a method for measurement of reader performance.
5. Results of retrospective reader studies to compare different screening strategies including 2DDM + synthetic 2D, DBT alone, 2DDM + limited tomo views.
6. Measurement of trial participant experience of DBT + 2DDM vs 2DDM.
7. Demonstration of the effectiveness of Artificial Intelligence in the analysis of DBT images.

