We have therefore considered changing the randomization ratio in favour of the intervention arm and decreasing the overall recruitment target. We conclude that the randomization ratio could be changed to 1:3 (control:intervention) and the overall target recruitment changed to 70,000. This would provide sufficient data to address the impact of DBT screening on interval cancer rates and cancer detection. We plan to augment the trial analysis with a further secondary analysis, comparing endpoints between our intervention group and figures from the national programme, using standardised incidence ratios.

Table 1. Estimate of numbers recruited in control and intervention groups to 03.2025, with a 1:3 randomization ratio from 01.2024

			Control	Intervention	Total
To 09.2023			18,000	18,000	36,000
To 12.23			20,000	20,000	40,000
01.24 - 03.25 @1:3	control	intervention			
1500/month	5625	16,875	25,625	36,875	62,500
2000/month	7500	22,500	27,500	42,500	70,000

4. Invasive cancer detection rates.

For a comparison of invasive detection rates (the first primary endpoint), if we posit 9 per thousand in the DBT arm and 7 in the control, we will have approximately 80% power with the totals assuming recruitment of 1,500 per month and in excess of 80% power with 2,000 per month (5% significance level, 2-sided testing). Thus even without the use of the routine screening data, we will have sufficient power for the first primary endpoints.

5. Interval cancer rates.

Assuming the national rate of interval cancers in the control group, 3.5 per 1000 over 3 years, and if we assume conservatively that the reduction is 25% less than the increase in invasive detection rates, we would anticipate a rate of 2 per 1000 in the intervention arm.

Our totals for recruitment of 1,500 per month would yield in excess of 90% power to detect this as significant (5% significance level, two-sided testing). Thus we will be powered for this too.

6. As noted above, we also propose to carry out age-standardised comparison of these endpoints with those observed nationally, since the latter give highly precise estimates of outcomes for usual care. However, we re-emphasise that the primary analyses will be the protocol-specified randomised trial comparisons.

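### The primary comparison is stated in two incompatible ways, and the stated power belongs only to the pooled DBT arm, not to the DBT+S2D comparison the objective names

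*Protocol*

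**What the plan says.** **DBT+S2D only.** The title, the synopsis and section 2.2 describe the intervention as DBT+S2D. The primary objective in 2.1 compares outcomes "in intervention (DBT + S2D) and 2DDM (standard care) groups".

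**DBT with either 2D image.** The primary aim in the introduction allows S2D or 2DDM. So do the mortality projection in 2.4, the economic evaluation in 2.5, and this primary end-point in 2.1: "Cost-effectiveness of screening with DBT + 2DDM or S2D vs screening with 2DDM". The synopsis gives the matching cost end-point for DBT+S2D alone.

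**The regimen changes during recruitment.** Section 4.1 says: "After the first 25,000 women have undergone 2DDM and DBT, women entered into the interventional arm will undergo DBT and S2D". The section on risk from ionising radiation describes the same first phase as the first 50,000 women across both arms. It then proposes to stop 2DDM in the intervention group, with no date or number.

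**Power.** Section 2.3 (item 4), repeated in section 3, says: "if we posit 9 per thousand in the DBT arm and 7 in the control, we will have approximately 80% power" at 1,500 a month, and "in excess of 80% power with 2,000 per month (5% significance level, 2-sided testing"). The totals are the full arms in Table 1. Item 6 adds that the primary analyses are the randomised comparisons.

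**Secondary objective 1** in 2.1 is: "To demonstrate non-inferiority of DBT + S2D compared to DBT + 2DDM".

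**The concern.** A reader cannot tell whether women imaged with DBT+2DDM belong to the primary comparison. If they do, the result is for a mixed regimen that is mostly DBT+2DDM under section 4.1, and it should not be reported as the DBT+S2D answer that the title promises. If they do not, the protocol gives no power for the comparison it names. While both readings stand, the choice could be made after results are seen.

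The same switch affects secondary objective 1. Women are not randomised between DBT+S2D and DBT+2DDM. Comparing detection rates between the two regimens would compare earlier with later recruits in one arm, over a period in which two sites join and the allocation ratio changes.

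**Working it through.** **Inputs.** Rates of 9 v 7 per 1000 for invasive detection and 3.5 v 2.0 per 1000 for interval cancers; two-sided 5% (2.3, items 4 and 5). Control and intervention totals of 25,625 and 36,875 at 1,500 a month, or 27,500 and 42,500 at 2,000 a month; 20,000 per arm at 12.2023, then 1:3 (Table 1). Switch after 25,000 intervention women (4.1).

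**Formulas.** With difference d,
- SE1 = √[p_c(1−p_c)/n_c + p_i(1−p_i)/n_i]
- SE0 = √[p̄(1−p̄)(1/n_c + 1/n_i)], where p̄ is the weighted mean rate
- unpooled power = Φ(d/SE1 − 1.96)
- pooled power = Φ((d − 1.96·SE0)/SE1)

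No figure here allows for randomisation by clinic.

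**Step 1: the plan's own figure.** Whole arms, 9 v 7 per 1000:
- 1,500/month: SE1 = 0.716 and SE0 = 0.733 per 1000. Unpooled power is Φ(2.792 − 1.96) = 79.7%; pooled 78.5%. Stated: about 80%.
- 2,000/month: unpooled 83.7%, pooled 82.3%. Stated: above 80%.

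For interval cancers at 1,500/month the whole arms give 93.0% unpooled and 94.2% pooled, against a stated figure above 90%. All of these reproduce.

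**Step 2: how many women have each regimen.** 25,000/36,875 = 68% and 25,000/42,500 = 59% have DBT+2DDM. DBT+S2D women number 36,875 − 25,000 = 11,875, or 42,500 − 25,000 = 17,500. The intervention arm goes from 20,000 to 25,000 at 1:3, which adds 5,000/3 = 1,667 controls, so 21,667 controls precede the switch. Concurrent controls are 25,625 − 21,667 = 3,958, or 27,500 − 21,667 = 5,833.

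**Step 3: power if only DBT+S2D women counted, 9 v 7 per 1000** (unpooled / pooled). The switch points of 20,000 (the projected arm size at 12.2023) and 12,500 are assumptions.

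| Switch at | Recruits/month | DBT+S2D women | Concurrent controls | Power, concurrent | Power, all controls |
|---|---|---|---|---|---|
| 25,000 | 1,500 | 11,875 | 3,958 | 24.3% / 20.5% | 50.7% / 54.2% |
| 25,000 | 2,000 | 17,500 | 5,833 | 33.5% / 29.0% | 63.0% / 64.9% |
| 20,000 | 1,500 | 16,875 | 5,625 | 32.5% / 28.1% | 60.9% / 62.8% |
| 20,000 | 2,000 | 22,500 | 7,500 | 41.2% / 36.4% | 69.9% / 70.8% |
| 12,500 | 1,500 | 24,375 | 13,125 | 56.1% / 53.2% | 70.7% / 70.9% |
| 12,500 | 2,000 | 30,000 | 15,000 | 63.0% / 59.9% | 76.9% / 76.6% |

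The all-controls column borrows controls recruited before any woman counted in the intervention group, many of them at 1:1.

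**Step 4: interval cancers, 3.5 v 2.0 per 1000, switch at 25,000** (unpooled / pooled). Concurrent controls: 31.0% / 40.3% at 1,500/month and 42.8% / 52.7% at 2,000/month. All controls: 77.6% / 71.0% and 86.4% / 83.5%.

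**Step 5: secondary objective 1 as an unpaired comparison.** At 9 per 1000 in both groups, 25,000 v 11,875: SE = √[0.009 × 0.991 × (1/25,000 + 1/11,875)] = 1.05 per 1000. The 95% half-width is 1.96 × 1.05 ≈ 2.1 per 1000, about the same as the assumed DBT gain of 9 − 7 = 2.

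**Step 6: the two statements of the switch.** 25,000 intervention women and 50,000 women in all agree at 1:1. Under Table 1 they do not: after 40,000 women, the next 10,000 at 1:3 add 7,500 to the intervention arm, so the 50,000th woman comes when that arm has 27,500.

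**The case against.** The stated power is correct for what it describes. Section 2.3 refers to the DBT arm, uses the randomised totals and says the randomised comparisons are primary. Sections 2.3 and 3 openly describe the recruited intervention group as a mix of 2DDM and synthetic 2D. No text leaves out the first-phase women. All of this stands. A reader might infer that the trial's real power is 20-65% and not 80%. The documents do not support that: those figures are for a DBT+S2D-only analysis that the protocol names in its objective but never sets out.

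The switch point is also uncertain. The 25,000 is a written rule and not an observed count, Table 1 projects only 20,000 intervention women at 12.2023, and the radiation section allows an earlier stop. This stands too, and is why a range is shown. Even so, no switch point tried from 12,500 to 25,000 reaches 80% for invasive detection.

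On secondary objective 1, a reader might infer that the trial cannot exclude loss of the whole DBT gain. That holds only for an unpaired early-v-late comparison. The introduction says synthetic images are produced for all intervention women, raw images are stored for reader studies (5.2), and retrospective reader studies are planned. First-phase women could therefore be read both ways. The protocol does not say which route the objective takes. The choice of margin may properly sit in an analysis plan that is not shown, and its absence is not held against the protocol.

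**Conclusion.** The point holds as an inconsistency in the primary comparison. The stated power is right for the whole randomised arm, ignoring clustering, and does not carry over to the DBT+S2D comparison that the title and objective name.

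If DBT+S2D alone were meant and the switch came at 25,000, power for invasive detection would be about 20-33% with concurrent controls or 51-65% with all controls. For interval cancers it would be 31-53% or 71-86%, against a stated figure above 90%. With a switch at 20,000, invasive detection would have 28-41% or 61-71%; at 12,500, 53-63% or 71-77%. These ranges rest on the protocol's assumed rates, both recruitment speeds and both variance formulas.

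This is a should-fix. The randomised comparison remains valid; what is unsettled is which regimen its result describes.

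**What to change.** - In the synopsis, 2.1, 2.2 and 2.3, name one primary comparison: DBT with either 2D image v 2DDM, whole randomised arms. The stated power belongs to this.
- State the actual number of intervention women imaged with DBT+2DDM, and reconcile section 4.1 with the radiation section on when the switch took place.
- Make DBT+S2D v concurrent 2DDM a named secondary estimate with its own stated power.
- For secondary objective 1, either specify a paired reading of the synthetic images produced for all intervention women, or replace the aim of demonstrating non-inferiority with estimation and a 95% CI. In the second case, compare each regimen with its own concurrent controls and report the ratio of the two DBT-v-control ratios.

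The cost is protocol wording and one stratified analysis, plus a paired reading if that route is chosen. The downside is that the S2D-specific result becomes an estimate and not a powered test.
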